5. METHODS

5.1 Study parameters/endpoints

5.1.1 Main study parameter/endpoint

Number of ongoing pregnancies, conceived in the time window between randomization up to and including month 6 of intervention use. Ongoing pregnancy is defined as a visible embryonic heartbeat at ultrasound from 10-12 weeks of gestation onwards.

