5.3 Study procedures

Couples matching the inclusion criteria will be asked to participate in the trial. If after diagnostic work up the diagnosis infertility for the couple remains, both are asked for informed consent. After signing informed consent, the male patient will be randomised and allocated to Impryl® or placebo (double blinded).

Medication

Patients can directly start using the food supplement or placebo. Impryl® or placebo will be taken for a total duration of 6 months and will be directly stopped after having a positive pregnancy test.

Baseline characteristics

Patients are asked to report on these characteristics by a short questionnaire. Patients will receive an automatic email invitation directly after randomisation and are asked to provide this information online in the Castor database system

Lifestyle and outcome characteristics

Patients will be asked once every month to report on occurrence of pregnancy (with date of positive test), changes in weight and diet, changes in habit of smoking and drug or alcohol use, occurrence of fever and change in activities increasing scrotal temperature (hot baths, sauna, race cycling). Furthermore patients are instructed about taking note of the total amount of consumed study medication (used boxes and tablets). There is a question about the occurrence of adverse events. Patients will receive an automatic email and are asked to provide this information online in the Castor database system. When a pregnancy has been reached during the 6 months use of study medication the monthly questionnaires will be stopped, because there is no more necessity to record on lifestyle changes and treatment compliance.

Semen analysis

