If there is a clinical pregnancy in fertility patients, a routine (standard care) ultrasound will be performed in the first trimester between 5 to 9 weeks to determine the viability. Also routine (standard care) is an ultrasound around 10-12 weeks to estimate the due date. To limit the amount of extra site visits to zero, we decided that this 'due date' ultrasound at 10-12 weeks of pregnancy is enough for determining the primary outcome. The ultrasound can be made in the midwife practice. Information about the outcome of this ultrasound is reported in the 15-months questionnaire.

Questionnaire pregnancy/treatment outcome

To allow follow-up for treatment and pregnancy outcome, all couples will receive an automatic email with invitation for a short questionnaire 15 months after inclusion. They will receive questions about fertility treatment and pregnancy outcome (ability to achieve a pregnancy, occurrence of miscarriage or childbirth, date of delivery, gestational age, mode of delivery, complications of delivery, birth weight and sex of neonate). An email will be sent if the questionnaire is not returned after one month. If there is no reaction to the reminder email, either the patient or his general practitioner will be contacted by telephone to answer follow-up questions.

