7. STATISTICAL ANALYSIS

All data will be analyzed on an intention-to-treat basis. Data of patients who are lost to follow-up, will be included in their randomised group

will be included in their randomized group:

- Patients who are lost to follow-up during the treatment period are considered not to have achieved a pregnancy.
- Patients, who are lost to follow-up right after achieving a pregnancy of less than 8 weeks of gestation, are considered not to have achieved an ongoing pregnancy
- Patients, who are lost to follow-up right after achieving a pregnancy of 8 or more weeks of gestation, are considered to have achieved an ongoing pregnancy.

In addition, a per-protocol analysis will be performed for the primary outcome and the secondary outcomes overall pregnancy number, time to pregnancy, number of miscarriages and live birth rate.

Descriptive statistics will be calculated to check for major dissimilarities between study groups with respect to baseline information. Baseline data will be described quantitatively. For continuous variables, we will examine the distribution of the observations, and if normally distributed we will summarise them as means with standard deviations (SDs). If they are not normally distributed, then medians and inter-quartile ranges (IQRs) will be reported. For dichotomous data, we will provide counts and proportions.

The primary outcome variable 'ongoing pregnancy' will be assessed as follows. The ongoing pregnancy percentages as observed in the trial will be presented for both treatment arms, overall, and separately for the three strata (i.e. EM, IUI, IVF/ICSI). In order to adjust for possible imbalances between the treatment groups, the pregnancy percentages and differences in pregnancy percentages between the experimental and control group, and the corresponding 95% confidence intervals will be estimated using a fixed effects binomial model with an identity link, including intervention, fertility treatment, centre and female age (centered). If this model does not converge, a logit link will be used.

Time to ongoing pregnancy will be evaluated by the Kaplan-Meier approach; differences between the two arms will be tested with the log-rank test. Similar analyses will be conducted per stratum (EM, IUI or IVF/ICSI). The other secondary outcomes (overall pregnancy number, number of miscarriages, live birth rate, fertilization rate, embryo-utilization rate) will be evaluated similarly to the primary outcome. Changes in semen

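### The 10-12 week scan that defines the primary outcome is collected once, by couple report at month 15, and couples lost before then are scored by an 8-week rule instead of the scan

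*Combined protocol and SAP*

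**What the plan says.** Section 5.1.1 sets the endpoint: "Ongoing pregnancy is defined as a visible embryonic heartbeat at ultrasound from 10-12 weeks of gestation onwards". Section 5.3 accepts a routine scan as the source: "this 'due date' ultrasound at 10-12 weeks of pregnancy is enough for determining the primary outcome. The ultrasound can be made in the midwife practice". It then says when the result reaches the trial: "Information about the outcome of this ultrasound is reported in the 15-months questionnaire". The Summary says the same.

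Before that, couples report pregnancy and the date of the positive test each month. The same section ends this contact early: "When a pregnancy has been reached during the 6 months use of study medication the monthly questionnaires will be stopped". The reason given is that lifestyle and compliance data are no longer needed. The next scheduled contact is the final one: "all couples will receive an automatic email with invitation for a short questionnaire 15 months after inclusion". Non-responders get a reminder e-mail after a month, and after that "either the patient or his general practitioner will be contacted by telephone to answer follow-up questions". Section 5.5 promises full follow-up for all patients but adds no contact point.

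The topics listed for the month-15 questionnaire cover pregnancy, miscarriage, childbirth, delivery date and gestational age. They do not name the 10-12 week scan, its date or the heartbeat.

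Section 7 has three rules for loss to follow-up. Couples lost in the treatment period count as not pregnant. Those "lost to follow-up right after achieving a pregnancy of less than 8 weeks of gestation" count as not ongoing. Those lost at 8 or more weeks count as ongoing. Section 1.3 expects minimal loss, gives no figure and makes no allowance for it.

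**The concern.** The event that decides the primary outcome happens in a window when the trial has no planned contact with the couple, and possibly at a practice that holds no trial records. The result then depends on a single questionnaire many months later. If that questionnaire and the chase fail, the couple is classified by a gestation cut-off that lies before the defining scan.

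Two things are at stake. First, true ongoing pregnancies may be counted as failures, which lowers both rates, shrinks the absolute difference and costs some power. Second, some pregnancies may be counted as ongoing with no scan behind them. Apart from missing couples, a miscarriage is defined in Section 5.1.2 as a loss before 16 weeks. A miscarriage reported at month 15 therefore need not show whether a heartbeat had been seen at 10-12 weeks. Time to ongoing pregnancy, which Section 5.1.2 ties to ultrasound confirmation, also needs a dated scan.

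**Working it through.** **1. The plan's own figure (Section 1.3).** Inputs: p0 = 0.20, p1 = 0.265, d = 0.065, n = 600 per arm, two-sided 5%. With p̄ = 0.2325 and q̄ = 0.7675:

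power = Φ{[d√n − 1.96·√(2p̄q̄)] / √(p0q0 + p1q1)}

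= Φ{[0.065 × 24.495 − 1.96 × 0.5974] / 0.5956} = Φ(0.707) = 0.760.

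The stated 76% is reproduced, and solving for n at 76% power gives 600 per arm.

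**2. Delay between scan and question.** A scan at 10-12 weeks of gestation is 8-10 weeks after conception, or 8/4.35 = 1.8 to 10/4.35 = 2.3 months. Conceptions in months 0 to 6 put the scan between about month 1.8 and month 8.3. The question comes at month 15, so the delay is 15 − 8.3 = 6.7 to 15 − 1.8 = 13.2 months.

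**3. Last known gestation of a couple who later drop out.** Assume a test turns positive at 4-5 weeks (the documents give no figure). It is reported at the next monthly questionnaire, up to 4.35 weeks later. Last contact then falls between 4 and about 9.35 weeks. With reports spread evenly over the month, the share arriving at 8 weeks or later is 0.35/4.35 = 8% (test at 4 weeks) to 1.35/4.35 = 31% (test at 5 weeks). Most such couples would be scored as not ongoing, and a minority as ongoing.

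**4. Which rule in Section 7 applies.**

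| Last known state | Score | Possible error |
|---|---|---|
| Pregnant, under 8 weeks | Not ongoing | True ongoing pregnancy missed |
| Pregnant, 8 weeks or more | Ongoing | Loss before the 10-12 week scan counted as success |
| Pregnant, lost inside the 6-month treatment period | Rule 1 says not pregnant; the 8-week rules can also apply | Order of precedence not stated |

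**5. Size.** The documents give no loss rate. Let f be the share of true ongoing pregnancies that stay unretrieved after the whole chase, equal in both arms and all scored as failures. The rates become 0.20(1 − f) and 0.265(1 − f), put into the formula in step 1.

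| f (assumed) | Rates | Difference | Power | Pregnancies mis-scored, placebo / Impryl | n per arm for 76% |
|---|---|---|---|---|---|
| 0 | 20.0% / 26.5% | 6.5 points | 76.0% | 0 / 0 | 600 |
| 2% | 19.6% / 26.0% | 6.4 | 74.9% | 2.4 / 3.2 | 616 |
| 5% | 19.0% / 25.2% | 6.2 | 73.2% | 6.0 / 8.0 | 641 |
| 10% | 18.0% / 23.9% | 5.9 | 70.3% | 12.0 / 15.9 | 687 |

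For each f this is an upper bound on the harm from missed successes, because step 3 shows that some of these couples would be scored as ongoing. The opposite error cannot be sized: the documents give no rate of loss between 8 weeks and the scan.

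Unequal loss would matter more. With 5% lost on placebo and 10% on Impryl, the rates are 19.0% and 23.85%, a difference of 4.9 points with 53.5% power. The reverse gives 7.2 points and 85.6%.

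**The case against.** The strongest defence is that month 15 is a sensible time and that little is lost. A conception at the end of month 6 reaches term at about 6 + 38/4.35 = 14.7 months (taking term as 38 weeks from conception), so the date fits the live-birth endpoint. A reported birth shows that the pregnancy passed 10-12 weeks, and delivery date with gestational age dates the conception. Recall of the scan therefore matters mainly for pregnancies that were lost and for dating the scan. A couple counts as lost only after e-mail, reminder and telephone or general-practitioner contact have failed. All of this stands, and it is why the effect is modest. It does not supply any contact near the scan. The fallback source is the man's general practitioner, for a scan of the woman. Section 5.3 also mentions a routine viability scan at 5-9 weeks, which could give the clinic a later gestation, but no rule says that its result is collected.

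A reader might go further and infer that every pregnant couple not reached at month 15 is scored as a failure, or that the rule for 8 or more weeks can hardly ever apply. Section 7 and the monthly reporting schedule do not support that: reports can arrive at up to about 9 weeks, and those couples are scored as ongoing. A reader might also infer that couples who conceive are the ones who leave follow-up. Nothing in the documents shows this. Pregnant couples do miss the remaining monthly questionnaires, but no couple has a scheduled questionnaire between month 6 and month 15, and all get the same final form and chase. With blinding, the documents also give no reason to expect unequal loss between arms.

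**Conclusion.** The primary outcome is captured once, late and by couple report. Couples lost in between are classified by an 8-week cut-off that can err in both directions and overlaps with the rule for loss during treatment. Failure is the likelier score, on the assumption that tests turn positive at 4-5 weeks.

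At an assumed final loss of 2-10% of ongoing pregnancies, equal in both arms, the cost is at most about 0.1 to 0.65 points of difference and 1 to 6 points of power. That dilutes the effect; it does not create a false positive. It falls on a design with 76% power and no allowance for loss, so an inexpensive remedy is worth having. The point is an improvement to data capture and does not show that the primary analysis is invalid.

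**What to change.** Add one automatic Castor e-mail at about 12-13 weeks of gestation, timed from the positive-test date already collected. Ask first whether the pregnancy continues, then for scan date, gestational age and heartbeat seen or not. Use the existing reminder and telephone chase. Keep the month-15 questionnaire as back-up and name the scan items, and the gestation at any loss, in it. It is still needed for late month-6 conceptions that test positive after the last monthly questionnaire.

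In Section 7, state which rule takes precedence for a pregnant couple lost inside the treatment period. Add a sensitivity analysis of the 8-week rule, for example scoring all such couples first as not ongoing and then as ongoing.

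The cost is a short amendment and one extra contact, with no extra visit, so the plan's aim of adding no site visits is kept. The e-mail goes to every couple reporting a positive test. That is more than the roughly 23% expected to have an ongoing pregnancy ((20% + 26.5%)/2 = 23.25%, or 279 of 1200). Some recipients will have miscarried, which is why the first question should be whether the pregnancy continues. The result remains self-reported.

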5.4 Withdrawal of individual subjects

Subjects can leave the study at any time for any reason if they wish to do so without any consequences. The investigator can decide to withdraw a subject from the study for urgent medical reasons. There are no specific criteria for withdrawal.

5.5 Follow-up of subjects withdrawn from treatment

As the statistical analysis is planned according to intention to treat principle, patients that violate the study protocol will be analysed in the group that they were allocated to. All patients will receive full follow-up.

5.6 Premature termination of the study

The principal investigator at the initiating centre Radboudumc, may temporarily or permanently discontinue the trial at a single site or at all sites for safety, ethical, compliance or other reasons. If this is necessary, the principal investigator will endeavour to provide advance notification to the site. If the site or trial is suspended or discontinued, the principal investigator will be responsible for ensuring prompt notification to the METC (CMO Arnhem Nijmegen). Where required by local regulations, the principal investigator will be responsible for informing the METC of trial or site discontinuation. In such cases, all trial data must be returned to the principal investigator at the Radboudumc.

6. SAFETY REPORTING

6.1 Temporary halt for reasons of subject safety

In accordance to section 10, subsection 4, of the WMO, the sponsor will suspend the study if there is sufficient ground that continuation of the study will jeopardise subject health or safety. The sponsor will notify the accredited METC without undue delay of a temporary halt including the reason for such an action. The study will be suspended pending a further positive decision by the accredited METC. The investigator will take care that all subjects are kept informed.

6.2 AEs, SAEs and SUSARs

6.2.1 Adverse events (AEs)

Adverse events are defined as any undesirable experience occurring to a subject during the study, whether or not considered related to Impryl®. All adverse events reported by the subject or observed by the investigator or his staff will be recorded.

6.2.2 Serious adverse events (SAEs)

A serious adverse event is any untoward medical occurrence or effect that

- results in death;
- is life threatening (at the time of the event);
- requires hospitalisation or prolongation of existing inpatients' hospitalisation;
- results in persistent or significant disability or incapacity;
- is a congenital anomaly or birth defect; or
- any other important medical event that did not result in any of the outcomes listed above due to medical or surgical intervention but could have been based upon appropriate judgement by the investigator.

An elective hospital admission will not be considered as a serious adverse event.

The investigator will report all SAEs to the sponsor without undue delay after obtaining knowledge of the events.

The sponsor will report the SAEs through the web portal *ToetsingOnline* to the accredited METC that approved the protocol, within 7 days of first knowledge for SAEs that result in death or are life threatening followed by a period of maximum of 8 days to complete the initial preliminary report. All other SAEs will be reported within a period of maximum 15 days after the sponsor has first knowledge of the serious adverse events.

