5.1.2 Secondary study parameters/endpoints

Number of pregnancies conceived in the optimal intervention time window, i.e. between start of month 4 till the end of month 6.

Overall number of pregnancies meaning the cumulative pregnancy number up to 9 months after start of intervention

Time to pregnancy defined as

- a) the time between start randomization and reaching ongoing pregnancy (confirmed by ultrasound)
- b) the time between start of fertility treatment during the study (EM, IUI, IVF/ICSI) and reaching ongoing pregnancy

Change in semen parameters in IUI/IVF/ICSI group based on pre-wash total motile sperm count (TMSC), leading to different fertility treatment categorisation (EM, IUI, IVF, ICSI), from a subpopulation of patients: Radboudumc patients and patients from other sites having pre-wash TMSC as standard procedure when semen is used for IUI or IVF/ICSI.

Improvement between Impryl® and control group in fertilization rate and embryo-utilization rate in IVF/ICSI group. Fertilization rate is defined as the percentage of oocytes with 0 PN or ≥ 2 PN after insemination (IVF) or injection (ICSI). Abnormal fertilization such as 3PN will be recorded, in case this percentage differs or increases in the study group. The embryo-utilization rate (EUR) is defined as the number of high quality embryos obtained, embryo's used at transfer plus the number of embryos frozen, divided by the number of zygotes obtained in a cycle. Due to the differences in embryo evaluation and embryo selection criteria for cryopreservation, we decided to measure the relative increase in fertilization and utilization rate observed for each clinic.

Number of miscarriages (defined as non-vital intra-uterine pregnancy before 16 weeks of gestation)

Live birth rate (beyond 24 weeks, defined as the birth of a living child) within study-period of 15 months

Adverse effects

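### Birth defects count as serious adverse events, but no form as described in the protocol asks about them, so their ascertainment would be unknown

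*Combined protocol and SAP*

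**What the plan says.** Section 6.2.2 uses the usual seriousness criteria, one of which is that the event "is a congenital anomaly or birth defect; or". Investigators must report SAEs once they learn of them, and the sponsor forwards them within 7 or 15 days.

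Section 5.3 describes two follow-up forms that could bring such an event to light.

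- **Monthly online form, sent to the man.** "There is a question about the occurrence of adverse events". The Summary limits it to six mailings. It can also end earlier: "When a pregnancy has been reached during the 6 months use of study medication the monthly questionnaires will be stopped".
- **Month-15 form.** Section 5.3 says that "all couples will receive an automatic email with invitation for a short questionnaire 15 months after inclusion". After treatment and whether a pregnancy was achieved, the items listed are "occurrence of miscarriage or childbirth, date of delivery, gestational age, mode of delivery, complications of delivery, birth weight and sex of neonate". Couples who do not answer get a reminder. After that, the man or his general practitioner is telephoned with the follow-up questions.

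Three other passages bear on the point.

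- Section 6.2.1: "Adverse events are defined as any undesirable experience occurring to a subject during the study". The Summary states that all participants are adult men, and the adverse events named in the Secondary Objectives are symptoms of the man.
- Section 5.1.2 defines miscarriage as a non-vital intra-uterine pregnancy before 16 weeks, and live birth as beyond 24 weeks.
- Section 6.4 plans no follow-up of adverse events in general, but keeps SAEs reportable until the end of the study. Section 7 says only that adverse events will be summarised.

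**The concern.** The protocol names a category of serious event and then describes no data collection that asks for it. The one adverse-event question is put to the man and ends before any term birth. The one form that reaches couples after birth asks for the newborn's weight and sex but not for malformation. Cases would therefore enter the database only if someone volunteers them.

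Two further gaps add to this. A pregnancy terminated because of an anomaly, or lost between 16 and 24 weeks, has no clear category among the listed endings. And because an adverse event is something that happens to the subject, one site could file a child's anomaly under the father while another decides that it is not an event of its subject at all.

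At stake is the meaning of the safety report. The trial aims to produce pregnancies, with a product intended to act on sperm, so readers will look for a line on the children. A small or zero count could mean few anomalies or few questions asked, and the data could not tell these apart.

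**Working it through.** **1. SAE criterion against the forms**

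| Form, as described | Sent to | When | Asks about anomalies? |
|---|---|---|---|
| Monthly questionnaire | Man | Up to 6 times, ends at pregnancy | General adverse-event question only |
| Month-15 questionnaire | Couple | 15 months after inclusion | Not among the listed items |
| Telephone fallback | Man or his general practitioner | After the reminder | Same follow-up questions |

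**2. Timing.** Assume 266 days from conception to term and 30.4375 days per month.

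- Earliest term birth: 266 / 30.4375 = 8.7 months after randomisation. This is later than the sixth monthly form, so the adverse-event question never follows a term birth.
- Latest term birth in the primary window (conception at the end of month 6): (6 × 30.4375 + 266) / 30.4375 = 14.7 months. The month-15 form is therefore well placed, but the latest infants would be only about (15 − 14.74) × 30.4375 ≈ 8 days old.

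**3. Plan's own figure.** Inputs from section 1.3: 600 per arm, 20% against 26.5%, two-sided alpha 5%. With pooled variance under the null:

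- SE0 = √(2 × 0.2325 × 0.7675 / 600) = 0.0244
- SE1 = √((0.20 × 0.80 + 0.265 × 0.735) / 600) = 0.0243
- Power = Φ((0.065 − 1.96 × SE0) / SE1) = 0.760

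The stated 76% reproduces. It is not in dispute and only confirms the inputs.

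**4. Pregnancies at issue**

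- Planned effect: 600 × 0.20 + 600 × 0.265 = 120 + 159 = 279
- No effect: 2 × 600 × 0.20 = 240

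**5. Expected anomalies if every outcome is asked about.** The documents give no prevalence, so it is assumed.

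| Assumed prevalence | 240 pregnancies | 279 pregnancies |
|---|---|---|
| 1% | 2.4 | 2.8 |
| 2% | 4.8 | 5.6 |
| 3% | 7.2 | 8.4 |
| 5% | 12.0 | 14.0 |

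**6. Expected count if cases must be volunteered.** Capture is also assumed. Expected count = 279 × prevalence × capture, and P(zero) = (1 − prevalence × capture)^279.

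| Capture | 2% prevalence | P(zero) | 3% prevalence | P(zero) |
|---|---|---|---|---|
| 10% | 0.6 | 57% | 0.8 | 43% |
| 25% | 1.4 | 25% | 2.1 | 12% |
| 50% | 2.8 | 6% | 4.2 | 1.5% |

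**7. What a zero would mean.** If all 279 outcomes were known, zero cases would exclude a rate above 1 − 0.05^(1/279) = 1.1% (one-sided 95%). With unknown capture it sets no such bound.

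**8. What full capture could show.** This is the power to detect a doubling, with 120 and 159 pregnancies, by the method of step 3 (a rough approximation at such small counts): 9% at a prevalence of 1%, 14% at 2%, 20% at 3% and 33% at 5%.

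**The case against.** The strongest reply is that a route for these events already exists. Section 6.2.1 records whatever the subject reports or the staff observe, section 6.2.2 obliges the investigator to report every SAE that comes to notice, and section 6.4 keeps this open until the end of the study. The month-15 form also raises childbirth and complications of delivery, which may prompt a couple to mention an anomaly. The forms themselves are not in the documents, only short descriptions of them. All of this stands, so the point must be limited to active questioning on the forms as described.

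Several stronger readings are tempting, but the documents do not support them.

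- **The trial cannot record birth defects.** The passive route shows otherwise.
- **The count will be close to zero.** This depends on assumed prevalence and capture. At 50% capture and 2-3% prevalence, 2.8 to 4.2 cases would be recorded.
- **A difference between arms would be missed because nobody asks.** It would probably be missed anyway. Full capture gives only about 9-20% power for a doubling at 1-3% prevalence.
- **The trial could not support its claim of no extra risk.** Section 8.4 makes a prospective ethics statement about participants, not a conclusion about offspring.
- **Offspring harm is the main plausible risk.** The Introduction proposes a beneficial mechanism and names no offspring hazard. Section 3.3 describes micronutrients at the recommended daily dose.

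The gap in pregnancy endings also has a partial answer: gestational age is collected, so some losses at 16 to 24 weeks could be recognised. Termination and its reason could not.

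**Conclusion.** The point holds in a limited form. A named SAE category is left to volunteered reports, and it is unclear whether a child's anomaly belongs to the randomised man. Completeness would be unknown, so the number in each arm could not be read as a rate, whether it is zero or four.

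The size is modest: about 240 to 279 ongoing pregnancies, and roughly 5 to 8 expected anomalies at an assumed 2-3%. These figures rest on the plan's own pregnancy rates, on an outside prevalence that the documents do not give, and on counting ongoing pregnancies rather than births. Pregnancies conceived after month 6 are left out. The primary outcome, its test and the stated objectives are unaffected. This is a cheap improvement to the safety data, and its yield is a descriptive count.

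**What to change.** 1. **Section 5.3.** Add two items to the month-15 questionnaire and its telephone fallback: whether a congenital anomaly was found before or after birth, with a description, and a complete list of pregnancy endings (miscarriage before 16 weeks, loss at 16-24 weeks, stillbirth, termination with reason, ectopic pregnancy, live birth).
2. **Section 6.2.2.** State that an anomaly in a fetus or child conceived in the study is recorded as an SAE under the randomised man.
3. **Section 7.** Tabulate anomalies descriptively by arm, with the number of pregnancies of known outcome as denominator and the number of unknown outcome beside it. Section 7 counts a couple lost to follow-up at 8 or more weeks of gestation as having an ongoing pregnancy. Such couples belong in the unknown column here. No test is needed.

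The cost is two items on an existing online form, one sentence and one table, with no extra visit. The downsides are a sensitive question, a few more SAE reports, and some work to confirm self-reports from records. Anomalies in infants born shortly before month 15 may still be missed, and the report should say so.
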